9 DURATION OF STUDY

Subjects can receive assigned study treatment for up to 1 year. Subjects may refuse the study treatment at any time. Subjects who complete the Treatment Period or discontinue study treatment, will enter the Follow-up Phase ([Section 5.2.4](#)) for a total 1 year. During the Follow-up Period, all subjects will be contacted by phone every 3 months (± 1 week) to determine whether they have experienced for several days, the following symptoms that could potentially be associated with delayed listeremia: fever or chills, headache, nausea, confusion or changes in alertness (see [Section 6.2.6](#) for Management of Listeria During the Follow-up Period).

9.1 Withdrawal/Discontinuation Criteria

Subjects may withdraw consent at any time for any reason or be discontinued from study treatment at the discretion of the Investigator should any untoward effect occur. In addition, a subject may be withdrawn by the Investigator or the Sponsor if enrollment into the study is inappropriate, the study plan is violated or for administrative and/or other safety reasons. Specific details regarding discontinuation or withdrawal are provided in [Section 9.1](#).

A subject may be discontinued from the study with no further follow-up or data collection for any of the following reasons:

- Screen Failure
- Subject Lost to Follow-Up

- Death
- Withdrawal of Consent by Subject
- Other (specify)

A subject may be discontinued from study treatment, but will continue to be followed for any of the reasons listed below:

- Confirmed Disease Recurrence
- Clinical Deterioration
- Adverse Event/Serious Adverse Event
- Sponsor Decision to Stop Study
- Withdrawal of Consent by Subject
- Investigator Decision
- Study Non-Compliance by Subject
- Subject has Positive Pregnancy Test

In all cases, the reason for and date of study discontinuation must be recorded in the eCRF and in the subject's medical records. The subject must be followed up to establish whether the reason was an AE, and, if so, this must be reported and monitored through resolution.

The Investigator must make every effort to contact subjects who discontinue the study prematurely or are lost to follow-up in order to schedule the end of therapy assessments. These attempts to contact such subjects must be documented in the subject's records. It is expected that three phone calls and sending a certified letter will be sufficient to establish diligence in efforts to contact the subjects.

All subjects who discontinue study treatment will continue to be followed and evaluated for recurrence as outlined in [Section 7.1](#), Schedule of Events, for up to 5 years or death.

9.2 Subject Replacement Strategy

Subjects will not be replaced.

10 ADVERSE EVENT MONITORING AND REPORTING PROCEDURES

All Investigators have the primary responsibility for AE identification, documentation, grading, and assignment of attribution to the study treatment. It is the responsibility of the

Investigator to supply the medical documentation needed to support expedited AE reports in a timely manner.

10.1 Definitions

Adverse event (AE): any untoward medical occurrence in a subject or clinical investigation subject administered a pharmaceutical product and which does not necessarily have to have a causal relationship with this treatment. An AE can therefore be any unfavorable and unintended sign (including an abnormal laboratory finding, for example), symptom, or disease temporally associated with the use of a medicinal product or protocol-specified procedure, whether or not considered related to the medicinal product or protocol-specified procedure. Any worsening (i.e., any clinically significant adverse change in frequency and/or intensity) of a preexisting condition that is temporally associated with the use of study treatment (ADXS11-001 or Placebo) is also an AE.

AE(s) may occur during the course of the study, from overdose (whether accidental or intentional), or from abuse and withdrawal.

AE(s) may also occur in screened subjects during any pre-allocation baseline period as a result of a protocol-specified intervention, including washout or discontinuation of usual therapy, diet, placebo treatment or a procedure.

Serious adverse event (SAE): any AE occurring at any dose or during any use of ADXS11-001 or Placebo that:

- Results in death
- Is life threatening
- Results in persistent or significant disability/incapacity
- Results in or prolongs an existing inpatient hospitalization
- Is a congenital anomaly/birth defect
- Is a new cancer (that is not a condition of the study)
- Is associated with an overdose
- Is another important medical event

Recurrence of the cancer under study is not considered an AE unless it results in hospitalization or death.

Overdose: any dose exceeding the prescribed dose by 100%. No specific information is available on the treatment of overdose of ADXS11-001. In the event of an overdose, the subject should be observed closely for signs of toxicity. Appropriate supportive treatment

should be provided if clinically indicated. If an AE(s) results from the overdose of ADXS11-001, the AE is reported as a SAE(s), even if no other seriousness criteria are met. An overdose without any associated clinical symptoms or abnormal laboratory results is reported as an AE.

10.2 Assessing and Recording Adverse Events

AEs will be recorded and assessed from the time the informed consent form is signed through 30 days past last dose. Beyond that point, AEs related to the signs and symptoms of listeremia should be assessed and reported during the *Lm* surveillance period. Events will be recorded on the AE eCRF. AEs will also be assessed to determine if it meets the definition of “serious.” In the event that an AE meets the criteria for “serious” the appropriate SAE form will be completed and the event reported in accordance with the required time period. The reporting timeframe for SAEs is described in [Section 10.2.5](#).

10.2.1 Evaluating Adverse Events

An Investigator who is a qualified physician will evaluate all AEs according to the NCI CTCAE v 4.03. Any AE that changes CTCAE grade over the course of a given episode will have each change of grade recorded on the AE eCRF. In these cases, when the intensity of an AE changes over time for a reporting period (e.g., between visits) each change in intensity will be reported as an adverse event until the AE resolves. For example, 2 separate AEs will be reported if a subject experiences Grade 1 diarrhea for 3 days, meeting the definition of an AE, and then after 3 days the AE increases to a Grade 3 intensity that lasts for 2 days and then resolves. The Grade 1 event will be reported as an AE with a start date equal to the day the event met the AE definition and a stop date equal to the day that the event increased in intensity from Grade 1 to Grade 3. The Grade 3 event will also be reported as an AE with the start date equal to the day the event changed in intensity from Grade 1 to Grade 3 and a stop date on the day that the event changed intensity again or resolved. For analysis purposes, this will be considered one AE for this subject and the maximum intensity will be recorded.

When possible, AEs should be described in terms of a change in the baseline status or with a diagnosis or summary term rather than as individual symptoms.

Criteria for Determining AE Severity: The descriptions and grading scales found in the revised NCI CTCAE v 4.03 will be utilized for AE reporting.

Criteria for Determining AE Causality: The following attribution categories must be used in assessing the relationship between the AE and the study treatment: If the Investigator does not know whether or not the investigational agent caused the event, then the event will be handled as “related to investigational agent.”

RELATIONSHIP	ATTRIBUTION	DESCRIPTION
Unrelated to investigational agent/intervention	Unrelated	The AE is clearly NOT related to the study treatment
	Unlikely	The AE is doubtfully related to the study treatment
Related to investigational agent/intervention	Possible	The AE may be related to the study treatment
	Probable	The AE is likely related to the study treatment
	Definite	The AE is clearly related to the study treatment

10.2.2 Laboratory Test Abnormalities

Laboratory abnormalities that constitute an AE in their own right (are considered clinically meaningful, induce clinical signs or symptoms, require concomitant therapy or require changes in study treatment), should be recorded on the AE CRF. Whenever possible, a diagnosis, rather than a symptom should be provided (e.g., anemia instead of low hemoglobin). Laboratory abnormalities that meet the criteria for AEs should be followed until they have returned to normal or an adequate explanation of the abnormality is found. When an abnormal laboratory or test result corresponds to a sign or symptom of a previously reported AE, it is not necessary to separately record the laboratory/test result as an additional event.

Laboratory abnormalities that do not meet the definition of an AE should not be reported as AEs. A Grade 3 or 4 (severe) event, as per CTCAE V4.03, does not automatically indicate a SAE unless it meets the definition of serious, as defined in [Section 10.1](#) “Definitions” and/or as per the Investigator’s discretion.

10.2.3 Reporting Abnormal Test Findings

The criteria for determining whether an abnormal test finding should be reported as an AE are as follows:

- Test result is associated with accompanying symptoms; and/or
- Test result requires additional diagnostic testing or medical/surgical intervention: and/or
- Test result leads to a change in study dosing or discontinuation from the study, significant additional concomitant drug treatments, or other; and or
- Test result is considered to be an AE by the Investigator or sponsor

Merely repeating an abnormal test, in the absence of any of the above conditions does not constitute an AE. An abnormal test result that is determined to be an error does not require reporting as an AE.

10.2.4 Reporting Events Related to Immune Cell Activation

The most relevant AEs to consider under this category are high-grade hypotension (refractory to fluids and vasopressors) and high-grade hypoxia. In the prior version of this protocol, these events were included under the term “cytokine release syndrome” (CRS) along with nausea, headache, tachycardia, rash, and shortness of breath as per NCI CTCAE v 4.03 criteria. However, the description and grading scales for CRS in the NCI CTCAE v. 4.03 are not adequate to appropriately capture the toxicity associated with ADXS11-011, as per a recent communication from FDA. Investigators therefore are discouraged from using umbrella terms such as “cytokine release syndrome” or “infusion reaction” and are instead strongly encouraged to list each symptom and associated Grade individually.

Considering these communications with FDA, > Grade 3 hypotension and >Grade 3 hypoxia, along with other high-grade organ toxicities, will be considered Events of Special Interest and for which new guidelines for grading and management have been developed (Table 6.1-6.4). These are intended to be guidelines for the investigators, who will treat patients according to institutional recommendations.

10.2.5 Immediate Reporting of Serious Adverse Events to the Sponsor

Any SAE, or follow up to a SAE, including death due to any cause other than recurrence of the cancer under study that occurs to any subject from the time the consent is signed through 30 days past last dose, , whether or not related to ADXS11-001. Beyond that point, SAEs related to the signs and symptoms of listeremia should be assessed and reported during the 1-year *Lm* surveillance period. SAEs must be reported within 24 hours to the Sponsor at Syneos Health Clinical Pharmacovigilance (Attn: Syneos SAE Reporting; [contact] or email: [contact]

Additionally, any SAE, considered by an Investigator who is a qualified physician to be related to ADXS11-001 that is brought to the attention of the Investigator at any time outside of the time period specified above also must be reported immediately to the Sponsor.

SAE reports and any other relevant safety information are to be forwarded to Syneos Health Clinical Pharmacovigilance (Attn: Syneos SAE Reporting; [contact] or email: [contact]).

All reports of overdose with AE(s) must be reported within 24 hours to Syneos Health Clinical Pharmacovigilance (Attn: Syneos SAE Reporting; [contact] or email: [contact]).

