2.1.8.3 GOG-0265: Phase 2 Evaluation of ADXS11-001 in Recurrent, Refractory Cervical Cancer

2.1.9 Rationale for ADXS11-001 Dose Selection/Regimen/Modification

The dose regimen for both placebo and ADXS11-001 consists of a Prime Phase followed by a Maintenance Phase:

- Prime Phase = 1 dose administered q3 weeks for a total of 3 doses followed by;
- Maintenance Phase = 1 dose administered q8 weeks for a total of 5 doses

Those subjects who complete the 12-month treatment period (Prime + Maintenance Phases) may receive a total of 8 doses of ADXS11-001 at 1×10^9 CFU or placebo.

The recommended Phase 2 dose and the Prime Phase schedule were determined by safety and efficacy results from the Phase 1 and 2 studies (described in [Section 2.1.8.1](#) and [2.1.8.2](#), respectively). The Maintenance Phase of the study was included based on the 2 fundamental actions of *Lm*-LLO immunotherapy; (1) the generation of antigen specific lymphocytes; (2) and a reduction in the immune tolerance of the TME resulting from a reduction in the relative percentage and immune-suppressive function of Tregs and MDSCs in the TME. [REDACTED]

[REDACTED] In addition, the beneficial reduction of immune tolerance within the TME, attributable to the secretion of LLO, decreases as well. It is not known how long this effect persists after a single treatment with ADXS11-001, but clinical data suggest that this effect is not permanent. [REDACTED]

[REDACTED] Furthermore, a completed study in the adjuvant treatment of canine osteosarcoma demonstrated that after 2 months the antigen-specific T-cell response returns to baseline and that doses administered every 2 months were able to maintain elevated levels of T-cells [29]. Based on the previous studies completed in LACC the events of progression or recurrence, particularly in subjects with high risk disease, often occur within the first 12 months so therefore the Prime and Maintenance Phase dosing over a 12-month treatment period is hypothesized to be sufficient and able to potentially provide additional benefit to the subject.

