5.2 Randomization and Treatment Plan

Subjects must initiate the Screening period within 14 weeks after the completion of CCRT (inclusive of brachytherapy, when applicable). The Screening Period is 28 days in duration and all examinations and assessments required by the protocol are expected to be completed within this period. Clinical laboratory assessments must be completed no more than 3 days prior to randomization to ADXS11-001 or placebo.

Eligible subjects will be randomized 1:2 to Arm A (placebo) or Arm B (ADXS11-001).

Study treatment (ADXS11-001 or placebo) will be administered on Day 1 of the Week 1 visit. Study treatment may be administered ± 3 days within Day 1 of each scheduled infusion for subsequent visits (e.g. Week 4, Day 1 and Week 7, Day 1 visits).

- Arm A: Placebo administered IV over approximately [REDACTED] every 3 weeks (Weeks 1, 4 and 7 only) for 3 doses (Prime Phase), thereafter, subjects will receive an additional dose every 8 weeks (Weeks 15, 23, 31, 39, and 47) for 5 doses (Maintenance Phase). The *total treatment* period will be approximately 1 year.
- Arm B: ADXS11-001 administered IV over approximately [REDACTED] every 3 weeks (Weeks 1, 4 and 7 only) for 3 doses (Prime Phase), thereafter, subjects will receive an additional dose every 8 weeks (Weeks 15, 23, 31, 39, and 47) for 5 doses (Maintenance Phase). The *total treatment* period will be approximately 1 year.

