- 4 Screening evaluations will be performed within the 28 day screening period, unless otherwise specified.
- 5 At every study treatment infusion, the indicated procedures will be performed within the specified window(s).
- 6 Informed Consent must be obtained prior to conducting screening evaluations.
- 7 Concomitant therapies and procedures will be collected from the time informed consent is signed through 30 days past last dose, and should be recorded in the eCRF.
- 8 Pretreatment prophylactic medication administration and IV hydration must be completed at least [REDACTED] before each study treatment infusion. The prescribed dosage of the selected prophylactic medications will be at the discretion of the Investigator.
- 9 Study treatment (ADXS11-001 or placebo) may be administered ± 3 days within Day 1 of each scheduled infusion. The assigned study treatment will be administered every 3 weeks for a total of 3 doses during the Prime Phase and every 8 weeks for a total of 5 doses during the Maintenance Phase.
- 10 All Subjects will receive a 7-day course of oral antibiotic therapy starting 72 hours after administration of each ADXS11-001 treatment, except for the last treatment where subjects will receive a 3 week oral antibiotic course (instead of the 7-day course) to be initiated 72 hours following the last dose of study treatment (administered at Week 47) or immediately upon discontinuation of study treatment.
- 11 All AEs/SAEs will be assessed from the time Informed Consent is obtained through 30 days past last dose. Beyond that point, report the signs and symptoms of listeremia during the *Lm* surveillance period. All AE/SAEs will be followed through resolution. All AEs/SAEs experienced must be recorded on the eCRF.
- 12 Physical Examinations (PEs) will be performed up to 3 days prior to the administration of study treatment to confirm safety criteria for study treatment administration are met. Focused physical examination to be performed during the Prime Phase on Weeks 4 and 7, and during the Maintenance Phase on the Week 23 visit. Full physical exams should be performed on all other visits during the treatment period. In the follow-up phase, full physical exams should be performed if a blood culture positive for *Lm* is reported. PEs may be performed more frequently, as clinically indicated.

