7.2.2 Clinical Procedures/Assessments

7.2.2.1 Adverse Event Monitoring

The Investigator or qualified designee will assess each subject to evaluate for potential new or worsening AEs as specified in the Schedule of Events and more frequently if clinically indicated. AEs will be recorded starting from the time that the first dose of study treatment is administered through the completion of the *Lm* surveillance period. Adverse and serious adverse events experienced during this period will be reported and recorded in the eCRF. Adverse experiences will be graded according to NCI CTCAE v 4.03 (see [Section 10.2](#)). Toxicities will be characterized in terms regarding seriousness, causality, toxicity grading, and action taken with regard to study treatment.

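### Three passages close general AE/SAE collection 30 days after the last dose although doses from Week 7 on are 56 days apart, and two other sections set a longer window

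*Combined protocol and SAP*

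**What the plan says.** **Collection window.** Section 10.2.5 has SAEs reported "from the time the consent is signed through 30 days past last dose", related or not. Section 10.2 says "AEs will be recorded and assessed from the time the informed consent form is signed through 30 days past last dose". Footnote 11 of the Schedule of Events (Section 7.1) agrees: "All AEs/SAEs will be assessed from the time Informed Consent is obtained through 30 days past last dose".

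**Dosing.** Section 2.1.9 states "Maintenance Phase = 1 dose administered q8 weeks for a total of 5 doses". Section 5.2 places the doses at Weeks 1, 4 and 7, then Weeks 15, 23, 31, 39 and 47. Visits after the first may move by 3 days either way.

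**Exceptions to the 30-day limit.**
- SAEs the investigator considers related to ADXS11-001 are reportable whenever they come to light (Section 10.2.5). If causality is not known, the event is handled as related (Section 10.2.1).
- Listeremia-related AEs and SAEs are collected through the *Lm* surveillance period (Sections 10.2 and 10.2.5).
- If an AE was the reason for stopping, it must be reported and followed (Section 9.1).
- AEs still present when a subject discontinues are followed under Section 10 (Sections 7.2.6.1.1 and 7.2.6.1.2).

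**Conflicting text.** Section 7.2.2.1 says "AEs will be recorded starting from the time that the first dose of study treatment is administered through the completion of the" *Lm* surveillance period. Section 7.2.6.1.3 asks sites to report any AEs arising in the Follow-up Phase. Neither has a 30-day limit or a restriction to listeremia. Section 5.2.4.1, by contrast, confines surveillance-phase reporting to events potentially associated with listeremia.

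**Analysis.** Section 11.2.2 puts every subject who started treatment into the AE analyses and gives no time cutoff. The full SAP is described as a separate document.

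**The concern.** A window tied to the last dose works when it is at least as long as the dosing interval. Here it is shorter. Whether a dose was the last is known only later, so the status of an event on day 40 depends on what happens next. If another dose is given, the event is inside. If the subject stops or dies first, the earlier dose becomes her last and the event is outside. Capture then depends on continuing treatment, which is itself an outcome.

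Comparing the frequency and severity of AEs between regimens is a secondary objective (Section 1.2), and the Data Monitoring Committee receives AE tabulations by grade and arm (Section 10.3). If subjects stop at different rates or for different reasons in the two arms, selective capture could distort that comparison. Separately, sections that state different windows allow sites to follow different rules.

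**Working it through.** The check is calendar arithmetic on the dose weeks in Section 5.2 and the 30-day limit in Sections 10.2 and 10.2.5 and footnote 11.

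**1. Reproduce the stated interval.** Dose day = 7 × (week − 1) + 1.
- Weeks 1, 4, 7, 15, 23, 31, 39, 47 give days 1, 22, 43, 99, 155, 211, 267, 323.
- Successive intervals are 21, 21, 56, 56, 56, 56 and 56 days. The stated 8 weeks is reproduced, and Week 7 to Week 15 is also 56 days, so five intervals are affected.

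**2. Days that depend on a further dose.**
- 21-day intervals: 21 < 30, so none.
- 56-day intervals: 56 − 30 = 26 days (days 31 to 56), and 26/56 = 46%. Leaving out day 56, when the next dose is due, gives 25 days.

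**3. Visit windows.** If consecutive visits use opposite ends of ±3 days, the interval runs from 56 − 6 = 50 to 56 + 6 = 62 days.
- (50 − 30)/50 = 20/50 = 40%.
- (62 − 30)/62 = 32/62 = 52%.

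**4. Example.** The Week 15 dose falls on day 99, and its 30 days end on day 129. Take an event on day 99 + 40 = 139. A subject dosed at Week 23 (day 155) has a window running to at least day 155 + 30 = 185, so the event is inside. A subject who stops on day 150 has a window that closed on day 129, so the same event is outside unless an exception applies.

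**5. Scheduled reviews.** The Schedule of Events has AE review and imaging at Weeks 12 and 36. These fall (12 − 7) × 7 = 35 and (36 − 31) × 7 = 35 days after the preceding dose. If recurrence found at either visit ends treatment, that visit already lies past day 30.

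**6. What the exceptions leave.**
- The related-SAE rule does not cover non-serious AEs, even related ones.
- The reason-for-stopping rule covers only that AE.
- The rule for AEs present at discontinuation does not reach events already resolved.

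Still exposed, in subjects who stop or die before the next dose, are SAEs and deaths judged unrelated, and other non-listeremia AEs. Section 10.2.5 already leaves out deaths from recurrence of the cancer under study, so the deaths at issue there are those from other causes.

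**7. The passages side by side.** For an unrelated, non-listeremia event on day 40 in a subject who stops on day 51, Sections 10.2 and 10.2.5 and footnote 11 put it outside. Section 7.2.2.1 puts it inside. The start differs too: consent in the first group, first dose in Section 7.2.2.1.

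**The case against.** The strongest case is that little is lost in practice.

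- **Longer windows exist.** On Sections 7.2.2.1 and 7.2.6.1.3 alone there is no gap. True, but three passages say otherwise and Section 5.2.4.1 sides with them for the surveillance phase. This makes the problem partly one of contradiction; it does not remove it.
- **Events are recorded as they happen.** On day 40 nobody knows the dose was the last, SAEs are due within 24 hours, and no passage removes events already recorded. This stands. The real exposure is mainly unrelated events first learned of at or after stopping. Whether recorded events count depends on the separate SAP, which is not part of the text reviewed.
- **Deaths are counted elsewhere.** All deaths are DFS events whatever the cause (Section 11.2.6), and OS is a secondary endpoint. This stands: any understatement of deaths is confined to safety reporting.
- **Dosing is over.** Section 11 moved all subjects to End of Treatment by 31 July 2019, with one exception dosed into September. Protocol wording cannot now change collection during dosing, but the analysis rule can still be fixed.

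A reader might also infer that infusion toxicity in Arm B drives a bias. The documents do not support that route. Section 5.2.3.1 has these symptoms typically starting 2 to 4 hours after infusion and often resolving within 12 to 24 hours. Toxicity stopping limits are generally 7 days (Table 6.2) or 3 weeks from onset (Table 5), so most such decisions fall before day 31. Stopping could differ by arm in other ways, since only Arm B receives active trimethoprim/sulfamethoxazole and intolerance to it means discontinuation, but no rates are given.

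**Conclusion.** The point holds in a limited form. Under Sections 10.2 and 10.2.5 and footnote 11, 26 of the 56 days after each dose from Week 7 to Week 39 (46%; 40% to 52% with visit windows) are inside the general AE/SAE window only if another dose follows. The named exceptions narrow this, and Sections 7.2.2.1 and 7.2.6.1.3 contradict it. The percentages are shares of time, not of events or subjects. The primary DFS analysis is not affected.

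The size and direction of any between-arm bias in the AE comparison cannot be computed, because the documents give no AE or discontinuation rates by arm.

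Two larger figures might be inferred and should not be used:
- **That 46% of subjects stopped in Maintenance were past the window at End of Treatment.** This needs stopping to fall uniformly within dosing intervals. Section 11 says only that subjects were moved by 31 July 2019, not on one day, and does not say how many were then in Maintenance.
- **That 79% of an interval is uncovered after a surgical delay.** This adds a full 12 weeks to 8 weeks: (140 − 30)/140. Section 4.2.1.2 does not say when the 12 weeks start, and says only that a subject delayed beyond them may be discontinued. Counted from the last dose, the figure is (84 − 30)/84 = 64%, and either is an extreme case.

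**What to change.** Reconcile Sections 7.2.2.1, 7.2.6.1.3, 10.2 and 10.2.5 and footnote 11 of the Schedule of Events to one general AE/SAE window, the same in both arms. End it at the later of 30 days after the last dose and the End of Treatment or discontinuation visit, or at death if that comes before the visit. State one start point. Keep listeremia-related reporting and the reporting of related SAEs running beyond that date as now written. No day between the last dose and the discontinuation visit is then uncovered.

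Because dosing has ended, also state in the SAP that the AE comparison counts all AEs recorded up to that same date in both arms. Events that a site never recorded because it followed the shorter rule cannot be recovered this way.

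The cost is wording in the protocol and SAP. AEs are already reviewed at the End of Study or Early Discontinuation visit, so no visit is added. The small downside is a few more unrelated events to process.
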